6.4. Study Period/Treatment Period

6.4.1. Baseline/Day 1 Visit

- a. The following procedures will be performed at the Baseline/Day 1 Visit BEFORE dosing with investigational product:
- Ask the subject or observer (parent/legal guardian/other caregiver) when applicable to complete the Peak Pruritus NRS/Patient Reported Itch Severity Scale/Observer Reported Itch Severity Scale and PGIS/OGIS QD (preferably same time of day each day if applicable) before IP morning dose applied starting at Baseline/Day 1 and continuing through Day 28 and at Day 29.
 - Ask the subject or observer when applicable to complete the POEM, DLQI, CDLQI, IDQOL, and DFI.
 - Assess and record any changes in the subject's prior and concomitant medications since the Screening Visit (if Screening and Baseline are 2 visits); see [Section 5.8](#) for medications prohibited prior to Baseline/Day 1 and during the study.
 - Obtain and record medical history.
 - Obtain vital signs (temperature, respiratory rate, pulse rate, and BP) in the seated or supine position, after the subject has been sitting or lying calmly for a minimum of 5 minutes; assessment of vital signs should precede blood draw for clinical laboratory tests.
 - Measure height and weight.
 - Perform a disease focused physical examination of all AD involved skin (in treatable and non-treatable areas) and evaluate any current or reported symptoms for clinically significant changes.
 - Complete the ISGA. ISGA must be completed prior to CCI [REDACTED] the EASI assessment (Note: The ISGA score must be 2 or 3 at Baseline/Day 1 for subject to be eligible for the study).
[REDACTED]
 - Complete the EASI assessment, after completing the ISGA CCI [REDACTED]
[REDACTED]

- Calculate subject's Treatable %BSA.
- Confirm subject's eligibility based on the [Inclusion Criteria](#) and [Exclusion Criteria](#), including confirming acceptable methods of birth control for female subjects of childbearing potential.
- Assess and record any AEs/SAEs.
- Draw blood for clinical laboratory tests on Day 1 prior to initial dosing; assessment of vital signs should precede blood draw for clinical laboratory tests; testing includes serum chemistry and hematology.

Note: If the screening serum chemistry and hematology tests are performed within 15 days prior to Day 1, whether the Day 1 serum chemistry and hematology tests are to be performed will be at the discretion of Principle Investigator (PI) or designee.

At the discretion of the investigator or his/her designee, a topical lidocaine-based anesthetic (eg, lidocaine 4% cream) may be used prior to clinical laboratory sample collection to decrease potential discomfort to the subject. However, the skin must be thoroughly cleansed prior to blood sample collection. Use of a topical lidocaine-based anesthetic must be recorded in the Concomitant Medication eCRF.

- Perform a urine pregnancy test (female subjects of childbearing potential only) and confirm the subject has a negative urine pregnancy test result prior to randomization.
- Mark the subject's source documents to record the treatable AD areas (excluding the scalp) as identified by the investigator or his/her designee at Baseline/Day 1 and provide subject and/or parent/legal guardian with documentation of the designated treatment areas.
- A checklist of body areas currently affected by AD will be completed at the baseline/Day 1 visit. Location of skin lesions will be selected from a prepopulated listing of body locations.
- After PI's or designee's documented confirmation of eligibility, access IRT system to randomize subject to investigational product treatment.
- Access into IRT system to dispense the investigational products based on IRT randomization code.

- Weigh investigational product tube(s) before applying first dose; record investigational product tube(s) weight in subject's source documents.
- Wearing gloves, study staff will apply a layer of investigational product ointment (first dose) to all treatable AD lesions identified at Baseline/Day 1.
- The following procedures will be performed at the Baseline/Day 1 Visit AFTER dosing with investigational product:
 - Assess and record any AEs (including application site reactions) and SAEs.
 - Provide to subject and/or parent/legal guardian a sufficient number of tubes of investigational product for 1 week of dosing; ensure that all dispensed tubes are weighed, and weight is recorded in subject's source documents.
 - Instruct the subject and/or the parent/legal guardian that subject should not wipe investigational product off the skin, avoid occluding the treated areas, and refrain from swimming or bathing/washing the treated areas within 4 hours after application.
 - Dispense dosing diary and instruct the subject's parent(s)/legal guardian on use (ie, each time investigational product is applied). Instruct the subject and/or parent/legal guardian regarding all procedures for at home dosing beginning with the evening (PM) dose on Day 1 followed by BID dosing through Day 28, including how to complete the Dosing Diary, which will start at the Baseline/Day 1 Visit and continue BID through Day 28 (ie, each time investigational product is applied).
 - Contraception check: Confirm and document that proper contraception is being used for the female subject of childbearing potential and their partner as appropriate.
 - Review the schedule of upcoming study visits with the subject and/or parent/legal guardian and instruct them to return at the scheduled time for the Day 8 Visit.
 - Remind the subject and/or parent/legal guardian to bring all investigational product tubes (empty, partially used and unused) and the Dosing Diary to their next visit.

6.4.2. Day 8 (± 1 day), Day 15 (± 3 days) and Day 22 (± 3 days) Study Visit

The following procedures will be performed:

- Remind the subject or observer when applicable to complete the Peak Pruritus NRS/Patient Reported Itch Severity Scale/Observer Reported Itch Severity Scale (QD before investigational product is applied).
- Remind the subject or observer when applicable to complete the PGIS/OGIS, Patient Global Impression of Change (PGIC)/Observer Global Impression of Change (OGIC).
- Remind the subject or observer when applicable to complete the POEM, DLQI, CDLQI, IDQOL, DFI (these questionnaires will only be completed for Day 15 visit, not for Day 8 and Day 22 visit).
- Assess and record any changes in concomitant medications, including confirming that subject is not taking any prohibited medications.
- Assess and record any AEs (including application site reactions) and SAEs. For any AE occurring in the treated area, a body site check list will be used to report the AE locations.
- Obtain vital signs (temperature, respiratory rate, pulse rate, and blood pressure) (only for Day 15 visit, not scheduled for Day 8 and Day 22 visit) in the seated or supine position, after the subject has been sitting or lying calmly for a minimum of 5 minutes.
- Complete the ISGA. ISGA must be completed prior to CCI [REDACTED] EASI assessment.
- [REDACTED]
- Complete the EASI assessment, after completing the ISGA CCI [REDACTED]
- Calculate subject's Treatable %BSA.
- Update the documentation of treatable areas for any new AD lesions that appear after the Baseline/Day 1 Visit. The subject and parent/legal guardian (if applicable) will be

provided with documentation of the designated treatment areas, to ensure that previously treated areas which have resolved continue to be treated as required.

- Review Dosing Diary and assess compliance; re-educate the subject and/or parent/legal guardian if any missed doses have occurred.
- Collect returned tube(s) of investigational product from the subject and/or parent/legal guardian and weigh them. Weights will be recorded in subject's source documents.
- Access into IRT system to assign new tube(s) of investigational product (enough for 1 week of dosing) and weigh them prior to dispensing the tube(s) to subject and/or parent/legal guardian.
- Remind the subject and/or parent/legal guardian that investigational product must continue to be applied at home twice each day (am and pm), as instructed.
- Dispense dosing diary.
- Instruct the subject and/or parent/legal guardian that subject should not wipe investigational product off the skin, avoid occluding the treated areas, and refrain from swimming or bathing/washing the treated areas within 4 hours after application.
- Contraception check: Confirm and document that proper contraception is being used for the female subject of child bearing potential and their partner as appropriate.
- Review the schedule of upcoming study visits with the subject and/or parent/legal guardian, and instruct them to return at the scheduled time for the next visit.
- Remind subject and/or parent/legal guardian to bring all investigational product tubes (empty, partially used and unused) and the Dosing Diary to their next visit.

6.4.3. Day 29 (± 3 days) (End-of-Treatment)/Early termination Study Visit

In the event the Day 29 Visit must be delayed, eg, due to an unavoidable scheduling conflict, subject and/or parent/legal guardian will be instructed to continue blinded investigational product application BID through the evening before the day on which the rescheduled End-of-Treatment Visit is to occur. The following procedures will be performed at the Day 29/Early Termination Visit:

- Ask the subject or observer when applicable to complete Day 29 Peak Pruritus NRS/Patient Reported Itch Severity Scale/Observer Reported Itch Severity Scale, PGIS/OGIS scale if not already completed.
- Ask the subject or observer when applicable to complete the PGIC/OGIC, POEM, DLQI, CDLQI, IDQOL, DFI.
- Assess and record any changes in concomitant medications, including confirming that subject is not taking any prohibited medications.
- Assess and record any AEs (including application site reactions) and SAEs. For any AE occurring in the treated area, a body site check list will be used to report the AE locations.
- Urine pregnancy test (female subjects of childbearing potential only).
- Obtain vital signs (temperature, respiratory rate, pulse rate, and BP) in the seated or supine position, after the subject has been sitting calmly for a minimum of 5 minutes; assessment of vital signs should precede blood draw for clinical laboratory tests.
- Draw blood for clinical laboratory tests including chemistry and hematology (after having assessed vital signs).

Note: At the discretion of the investigator or his/her designee, a topical lidocaine-based anesthetic (eg, lidocaine 4% cream) may be used prior to clinical laboratory sample collection to decrease potential discomfort to the subject. However, the skin must be thoroughly cleansed prior to blood sample collection. Use of a topical lidocaine-based anesthetic must be recorded in the Concomitant Medication eCRF.

- Perform a full physical examination, evaluate any current or reported symptoms for clinically significant changes and report relevant AE if applicable.
- Complete the ISGA. ISGA must be completed prior to CCI [REDACTED] the EASI assessment.

• [REDACTED]

- Complete the EASI assessment, after completing the ISGA CCI [REDACTED]

- Calculate subject's Treatable %BSA based on all AD lesions present at Day 29, excluding the scalp.
- Review Dosing Diary and assess compliance.
- Collect Dosing Diary.
- Collect returned tube(s) of investigational product from the subject and/or parent/legal guardian and weigh them.
- Contraception check: Confirm and document that proper contraception is being used for the female subject of childbearing potential and their partner as appropriate.
- The participants who rolled over into study C3291027 without a Post Treatment Follow Up period prior to 21 Oct 2020 are considered completers in this study.

6.4.4. Unscheduled Visit

The procedures performed at an Unscheduled Visit will depend on the reason for the visit (some procedures may not apply).

- Assess and record any changes in concomitant medications, including confirming that subject is not taking any prohibited medications, as detailed in [Section 5.8.3](#).
- Obtain vital signs (temperature, respiratory rate, pulse rate, and BP) in the seated or supine position, preferably after the subject has been sitting or lying face up for a minimum of 5 minutes.
- Weigh investigational product tubes; record investigational product tubes weight in subject's source documents.
- Instruct the parent(s)/legal guardian regarding all procedures for at home dosing beginning BID dosing through Day 29 visit, including how to complete the dosing diary.
- Assess and record any AEs, including application site reactions, and SAEs.
- Review the schedule of upcoming study visits with the parent(s)/legal guardian and instruct them to return at the scheduled time.

6.4.5. Follow-up Contact/Follow Up Period

Follow-up contact will be done via a phone call on 7 (± 3) days and 31 (± 3) days after the End of Treatment/Early Termination Visit to capture any potential adverse events and to review (see the [Time Period for Collecting AE/SAE Information](#) section) and record concomitant medications and to confirm appropriate contraception usage (see the [Contraception](#) section).

6.5. Subject Withdrawal/Early Termination

Withdrawal of consent:

Subjects and/or parent(s)/legal guardian/legally acceptable representative who request to discontinue receipt of study treatment will remain in the study and must continue to be followed for protocol specified follow-up procedures. The only exception to this is when a subject specifically withdraws consent for any further contact with him or her or persons previously authorized by the subject to provide this information. Subjects should notify the investigator in writing of the decision to withdraw consent from future follow-up, whenever possible. The withdrawal of consent should be explained in detail in the medical records by the investigator, as to whether the withdrawal is only from further receipt of investigational product or also from study procedures and/or posttreatment study follow-up, and entered on the appropriate CRF page.

Lost to follow-up:

All reasonable efforts must be made to locate subjects to determine and report their ongoing status. This includes follow-up with persons authorized by the subject as noted above. Lost to follow-up is defined by the inability to reach the subject after a minimum of 2 documented phone calls, faxes, or e-mails as well as lack of response by the subject to 1 registered mail letter. All attempts should be documented in the subject's medical records. If it is determined that the subject has died, the site will use locally permissible methods to obtain the date and cause of death. If the investigator's use of a third-party representative to assist in the follow-up portion of the study has been included in the subject's informed consent, then the investigator may use a sponsor-retained third-party representative to assist site staff with obtaining the subject's contact information or other public vital status data necessary to complete the follow-up portion of the study. The site staff and representative will consult publicly available sources, such as public health registries and databases, in order to obtain updated contact information. If, after all attempts, the subject remains lost to follow-up, then the last-known-alive date as determined by the investigator should be reported and documented in the subject's medical records.

Subjects may withdraw from the study at any time at their own request, or they may be withdrawn at any time at the discretion of the investigator or sponsor for safety (see also the [Withdrawal From the Study Due to Adverse Events](#) section) or behavioral reasons, or the inability of the subject to comply with the protocol-required schedule of study visits or procedures at a given study site.

If a subject does not return for a scheduled visit, every effort should be made to contact the subject. All attempts to contact the subject and information received during contact attempts must be documented in the subject's medical record. In any circumstance, every effort should be made to document subject outcome, if possible. The investigator should inquire about the reason for withdrawal, request that the subject return all unused investigational, request that the subject return for a final visit, if applicable, and follow up with the subject regarding any unresolved adverse events (AEs).

If the subject withdraws from the study, and also withdraws consent for disclosure of future information, no further evaluations should be performed, and no additional data should be collected. The sponsor may retain and continue to use any data collected before such withdrawal of consent.

7. ASSESSMENTS

Every effort should be made to ensure that the protocol required tests and procedures are completed as described. However, it is anticipated that from time to time there may be circumstances outside of the control of the investigator that may make it unfeasible to perform the test. In these cases, the investigator will take all steps necessary to ensure the safety and wellbeing of the subject. When a protocol required test cannot be performed, the investigator will document the reason for this and any corrective and preventive actions that he or she has taken to ensure that normal processes are adhered to as soon as possible. The study team will be informed of these incidents in a timely manner.

For samples being collected and shipped, detailed collection, processing, storage, and shipment instructions and contact information will be provided to the investigator site prior to initiation of the study.

7.1. Efficacy Assessments

Clinical evaluations of atopic dermatitis will be performed by an experienced and certified physician, dermatologist, or medical professional. The evaluator must have received documented training to conduct the protocol AD specific clinical evaluations prior to performing these evaluations. To assure consistency and reduce variability, the same evaluator must assess all clinical evaluation of atopic dermatitis for any individual subject

throughout the study; a backup experienced and qualified, protocol trained evaluator will only be allowed and documented in case of emergency or special situation when the designated evaluator is unable to perform the evaluation. Identity (eg, initials) of the evaluator will be captured on the source documentation (eg, scale worksheet).

7.1.1. Calculation of Subject's Treatable %Body Surface Area (BSA)

The Treatable %BSA will be calculated for each subject at Screening, Baseline/Day 1, Days 8, 15, 22 and Day 29. The Treatable %BSA should be evaluated based on all AD lesions present on the day of the visit, excluding the scalp. Score 0 in the ISGA definition will not be evaluated as BSA while Score 1-4 will be.

Treatable %BSA is defined as the percentage of the subject's total BSA that is AD involved, excluding the scalp. To estimate the subject's Treatable %BSA, the investigator or his/her designee will use "handprint method", by which the area represented by the palmar (ie, outstretched) surface of the subject's hand with all five digits adducted together is approximately 1% of the subject's BSA, regardless of the subjects age.

7.1.2. Investigator's Static Global Assessment

The Investigator's Static Global Assessment (ISGA), a five point global static assessment of AD severity (Table 1), will be assessed at times specified in the [STUDY PROCEDURES](#) section of this protocol to characterize subjects' overall disease severity across all treatable AD lesions.

The assessment will be a static evaluation without regard to the score at a previous visit.

ISGA assessment during the study must be done by the investigator or his/her designee. Every effort should be made to ensure that all ISGA assessments for a given subject are done by the same qualified individual throughout the study.

Table 1. Investigator's Static Global Assessment

Score	Grade	Definition
0	Clear	Minor residual hypo/hyperpigmentation; no erythema or induration/papulation; no oozing/crusting
1	Almost Clear	Trace faint pink erythema, with barely perceptible induration/papulation and no oozing/crusting
2	Mild	Faint pink erythema with mild induration/papulation and no oozing/crusting
3	Moderate	Pink-red erythema with moderate induration/papulation with or without oozing/crusting
4	Severe	Deep or bright red erythema with severe induration/papulation and with oozing/crusting

CCI [REDACTED]

[REDACTED]

7.1.4. Eczema Area and Severity Index (EASI)

The EASI²⁶ quantifies the severity of a subject’s atopic dermatitis based on both severity of lesion clinical signs and the percent of BSA affected. EASI is a composite scoring of the degree of erythema, induration/papulation, excoriation, and lichenification (each scored separately) for each of four body regions, with adjustment for the percent of BSA involved for each body region and for the proportion of the body region to the whole body.

Percent BSA with Treatable AD: The number of handprints of AD skin in a body region can be used to determine the extent (%) to which a body region is involved with atopic dermatitis (Table 2).

Table 2 Handprint Determination of Body Region Surface Area

Body Region	Total Number of Handprints in Body Region*	Surface Area of Body Region Equivalent of One Handprint	Total Number of Handprints in Body Region*	
			Surface Area of Body Region Equivalent of One Handprint	
	≥8 years of age		2-7 years of age	
Head and Neck	10	10%	20	5%
Upper Limbs	20	5%	20	5%
Trunk (including axillae)	30	3.33%	30	3.33%
Lower Limbs (including buttocks)	40	2.5%	30	3.33%

*The number of handprints will be for the entire body region; these values will not be adjusted for exclusion of scalp from the BSA assessment.

Note: The age of cut-off is based on the age at time of informed consent.

The extent (%) to which each of the four body regions is involved with AD is categorized using a non-linear scaling method to a numerical area score according to the following BSA scoring criteria. See Table 3 on EASI Area Score Criteria.

Table 3. Eczema Area and Severity Index (EASI) Area Score Criteria

Percent BSA with Atopic Dermatitis in a Body Region	Area Score
0%	0
<10%	1
10% to <30%	2
30% to <50%	3
50% to <70%	4
70% to <90%	5
90% to 100%	6

Lesion Severity by Clinical Signs: The basic characteristics of atopic dermatitis lesions erythema, induration/papulation, excoriation, and lichenification provide a means for assessing the severity of lesions. Assessment of these four main clinical signs is performed separately for four body regions: head and neck, upper limbs, trunk (including axillae and groin) and lower limbs (including buttocks). Average erythema, induration/papulation, excoriation, and lichenification are scored for each body region according to a 4 point scale: 0 = absent; 1 = mild; 2 = moderate; 3 = severe. Morphologic descriptors for each clinical sign severity score are shown in [Table 4](#).

Table 4. Clinical Sign Severity Scoring Criteria for the Eczema Area and Severity Index (EASI)

Score		Description
Erythema (E)		
0	Absent	None; may have residual discoloration (post-inflammatory hyperpigmentation and/or hypopigmentation).
1	Mild	Light pink to light red
2	Moderate	Red
3	Severe	Deep, dark red
Induration/Papulation (I)		
0	Absent	None
1	Mild	Barely palpable to slight, but definite hard thickened skin and/or papules
2	Moderate	Easily palpable moderate hard thickened skin and/or papules
3	Severe	Severe hard thickened skin and/or papules
Excoriation (Ex)		
0	Absent	None
1	Mild	Slight, but definite linear or picked scratch marks or penetrating surface injury
2	Moderate	Moderate linear or picked scratch marks or penetrating surface injury
3	Severe	Severe linear or picked scratch marks or penetrating surface injury
Lichenification (L)		
0	Absent	None
1	Mild	Barely perceptible to slight, but definite thickened skin, fine skin markings, and lichenoid scale
2	Moderate	Moderate thickened skin, coarse skin markings, and coarse lichenoid scale
3	Severe	Severe thickened skin with very coarse skin markings and lichenoid scale
* The EASI will exclude scalp from the assessment/scoring		

In each body region, the sum of the Clinical Signs Severity Scores for erythema, induration/papulation, excoriation, and lichenification is multiplied by the Area Score and by the Body Region Weighting to provide a body region value, which is then summed across all four body regions resulting in an EASI score as described in Equation 1 and Equation 2:

Equation 1 (subjects aged ≥8 years old): $EASI = 0.1Ah(Eh+Ih+Exh+Lh) + 0.2Au(Eu+Iu+Exu+Lu) + 0.3At(Et+It+Ext+Lt) + 0.4Al(El+Il+Exl+Ll)$

Equation 2 (subjects aged 2-<8 years old): $EASI = 0.2Ah(Eh+Ih+Exh+Lh) + 0.2Au(Eu+Iu+Exu+Lu) + 0.3At(Et+It+Ext+Lt) + 0.3Al(El+Il+Exl+Ll)$

A = Area Score; E = erythema; I = induration/papulation; Ex = excoriation; L = lichenification; h = head and neck; u = upper limbs; t = trunk; l = lower limbs.

The EASI score can vary in increments of range from 0.0 to 72.0, with higher scores representing greater severity of atopic dermatitis. Considering the scalp will be excluded

from the EASI assessment in the present study, the maximum possible score will be less than 72.0 (modified EASI score).

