4.1. Inclusion Criteria

Subjects must meet all of the following inclusion criteria to be eligible for enrollment into the study:

1. Is male or female and the appropriate age in years (2 years and older) at time of informed consent/assent.
2. Has a clinical diagnosis of AD according to the criteria of Hanifin and Rajka (See [Appendix 2](#)).
3. Has AD involvement of $\geq 5\%$ Treatable BSA (excluding the scalp) at Baseline/Day 1.
4. Has an ISGA score of Mild (2) or Moderate (3) (excluding the scalp) at Baseline/Day 1.
5. Has adequate venous access to permit venipuncture for clinical safety laboratory sampling.
6. Female subjects of childbearing potential who have a negative urine pregnancy test at the screening visit and negative urine pregnancy test at the baseline visit prior to randomization. A female is of childbearing potential if, in the opinion of the investigator, she is biologically capable of having Children (includes any female who has experienced menarche and does not meet the criteria for females not of childbearing potential. Female subjects of non-childbearing potential must meet at least 1 of the following criteria:
 - a. Achieved postmenopausal status, defined as follows: cessation of regular menses for at least 12 consecutive months with no alternative pathological or physiological cause; have a serum follicle stimulating hormone (FSH) level confirming the postmenopausal state;
 - b. Have undergone a documented hysterectomy and/or bilateral oophorectomy;
 - c. Have medically confirmed ovarian failure.
7. Evidence of a personally signed and dated informed consent/assent document indicating that the subject [or parent(s)/legal guardian] has been informed of all pertinent aspects of the study.
8. Willing and able to comply with scheduled visits, treatment plan, laboratory tests and other study procedures.

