9.1. Sample Size Determination

The total sample size of 384 subjects in this study with a 2:1 randomization ratio (256:128) will provide approximately 90% power to detect a 12% difference of percent change from baseline in EASI total score at Day 29 between crisaborole arm and vehicle arm at the 0.05 (2-sided) significance level, CCI

Comparative EASI data relative to vehicle was not collected in previous crisaborole studies. The 12% treatment effect in EASI percent improvement was converted from the ISGA response in the Phase 3 studies using a linear regression equation that evaluated the relationship between ISGA response rate and EASI percent improvement from historical trial

data of other topical products (data on file). From the crisaborole Phase 3 pooled data, the ISGA response rate is 32.1 % for crisaborole and 21.8% for vehicle. The converted EASI percent improvement is 38.9% and 26.8% respectively. The difference of EASI percent improvement between crisaborole and vehicle is approximately 12%.

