6.1.1.1. Main Analysis

- Estimand strategy: Hypothetical.
- Analysis set: FAS.
- Analysis methodology: percent change from baseline in EASI total score at Day 29, will be analyzed using MMRM that includes treatment group, visit, and treatment group-by-visit interaction as factors and baseline value as a covariate. Within-subject variability will be accounted for using a random effect with the first-order autoregressive (AR(1)) covariance matrix.
- Intercurrent events and missing data: data after treatment discontinuation prior to Day 29 will not be considered. Missing values will not be explicitly imputed and will be assumed to be MAR.
- Reporting results:
 - Tables: The sample size, least-squares (LS) mean of percent change from baseline and 95% CI for each treatment, LS mean of difference and the corresponding 95% CI, and p-value will be presented at Day 29.

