6.1.1.2. Supplementary Analyses

An analysis using PPAS will be performed. It will use the same methodology and handling of intercurrent events as the main analysis.

6.1.2. TEAEs (including application site reactions) & SAEs and clinically significant changes in vital signs and clinical laboratory parameters

All safety analyses will be conducted on the Safety Analysis Set.

Pfizer standard will be utilized in reporting routine safety variables (Pfizer Safety Rulebook).

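### The primary MMRM gives both arms one covariance at 2:1 allocation on a lopsided percent-change endpoint, so its confidence interval is right only if the two arms are equally variable

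*Protocol*

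**What the plan says.** Protocol 4.1 sets two disease thresholds at baseline: at least 5% treatable body surface area, and a global score, "Has an ISGA score of Mild (2) or Moderate (3) (excluding the scalp) at Baseline/Day 1". It sets no minimum EASI.

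Protocol 7.1.4 defines the score by region weights, area scores and sign severities, and states that "The EASI score can vary in increments of range from 0.0 to 72.0", less in practice because the scalp is excluded. The primary analysis uses percent change in this score, summarised as a difference in means (SAP 2.1).

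For the model, SAP 6.1.1.1 says "Within-subject variability will be accounted for using a random effect with the first-order autoregressive (AR(1)) covariance matrix". Protocol 9.2.1 agrees. SAP 5.2.2 allows another structure only if there are convergence problems. Neither document mentions covariance parameters by treatment arm or empirical standard errors.

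The one supplementary analysis of the endpoint is in SAP 6.1.1.2: "An analysis using PPAS will be performed. It will use the same methodology and handling of intercurrent events as the main analysis". The subgroup analyses in SAP 6.4 repeat the main analysis.

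On size, Protocol 9.1 plans 256 crisaborole and 128 vehicle subjects and claims that this number "will provide approximately 90% power to detect a 12% difference of percent change from baseline in EASI total score at Day 29". On the planning means it says "The converted EASI percent improvement is 38.9% and 26.8% respectively", for crisaborole and vehicle in that order.

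**The concern.** A percent change is bounded on one side only. A subject who clears scores -100%. A subject who starts with a tiny EASI and develops one new lesion can double the score. The baseline covariate adjusts the mean for a low starting value, but not a variance that grows as the baseline shrinks.

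A less effective arm leaves more subjects away from the lower bound, so the arms could plausibly differ in spread. A model with one covariance then averages the two variances with weights of about 2:1 in favour of crisaborole, whereas the true variance of the difference weights the smaller vehicle arm more heavily. The primary confidence interval then has the wrong width. No other planned analysis of the mean difference would show this, because the per-protocol and subgroup analyses use the same model.

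A second, softer issue is influence: a few large increases from very low baselines can shift an arm mean noticeably.

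**Working it through.** **1. The planning figure.** Inputs from Protocol 9.1 are 256 and 128 subjects, a 12-point difference and two-sided 0.05. The SD is blacked out, so the stated 90% power cannot be reproduced independently. Solving for the SD that would give it:

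SD = 12 / [sqrt(1/128 + 1/256) × (1.960 + 1.282)] = 12 / (0.1083 × 3.242) ≈ 34.2 points.

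An SD of 30 would give 95.9% power and an SD of 40 would give 79.1%. No SD by arm is legible. The coverage results below do not depend on the SD's absolute value, only on the ratio between arms.

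**2. What the scoring allows** (Protocol 7.1.4, Tables 2 and 3, Equations 1 and 2). Take five handprints on the upper limbs (25% of the region, area score 2) with mild erythema and mild induration (sign sum 2, my reading of ISGA 2):

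- Baseline EASI = 0.2 × 2 × 2 = 0.8 in both age bands.
- One new lower-limb handprint (area score 1), sign sum 2, other lesions unchanged. Age 8 or over: 0.4 × 1 × 2 = 0.8, or +100%. Ages 2–7: 0.3 × 1 × 2 = 0.6, or +75%.
- The same patch with sign sum 3: +150% at age 8 or over, +112.5% at ages 2–7.
- Starting from a baseline of 5, the mild patch at age 8 or over adds 0.8/5 = 16%.

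Large jumps from one patch therefore need a very low baseline.

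**3. Effect of one shared variance.** Let r = vehicle SD / crisaborole SD, and let s be the crisaborole SD.

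- Model-based variance of the difference: s² × (2 + r²)/3 × (1/256 + 1/128) = s²(2 + r²)/256.
- True variance: s²(1/256 + r²/128) = s²(1 + 2r²)/256.
- Ratio of standard errors: sqrt[(2 + r²)/(1 + 2r²)]. Nominal 95% coverage becomes 2Φ(1.96 × ratio) − 1.

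| r | shared-variance SE / true SE | coverage |
|---|---|---|
| 0.8 | 1.076 | 96.5% |
| 1.0 | 1.000 | 95.0% |
| 1.2 | 0.942 | 93.5% |
| 1.5 | 0.879 | 91.5% |

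The value 1.2 comes from the planning means if spread is proportional to the mean remaining EASI: (1 − 0.268)/(1 − 0.389) = 0.732/0.611 ≈ 1.20. Proportional spread is an assumption. The values 0.8 and 1.5 are illustrations with no source in the documents.

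**4. Check with skewed data.** I used 20,000 simulated trials per setting, with percent change from a lognormal EASI ratio (log-scale SD 0.4 to 0.7) and a Day 29 two-sample comparison standing in for the MMRM.

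- Same distribution in both arms: the pooled test rejects in 4.9% to 5.1% of trials, with 2.6% to 2.9% in favour of crisaborole.
- Planning means, equal log-scale spread: pooled coverage is 93.4% to 93.7%, against about 94.7% to 94.8% with unequal variances.

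**5. Influence of one subject.** One vehicle subject at +300% moves the vehicle mean by 300/128 ≈ 2.3 points if that subject would otherwise have had no change. If the subject would otherwise have been at the planning mean, the shift is (300 + 26.8)/128 ≈ 2.6 points. That is about a fifth of the 12-point effect. From a baseline of 0.8, one new leg patch at age 8 or over needs a sign sum of 6 to reach +300% (0.4 × 6 / 0.8 = 3).

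**The case against.** The strongest reply is that nothing in the documents shows the arms will differ in spread. No SD is given by arm, and if crisaborole is the more variable arm the interval is conservative. Skewness alone does not break the two-sided test. All of this stands, and it makes the point conditional.

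The second reply is that the plan has other evidence. SAP 6.4 repeats the primary analysis by baseline ISGA, which separates the milder subjects. SAP 5.2.2 plans SD, median and range, which would expose extreme values. EASI-50 and EASI-75 (SAP 6.2.7) and the ISGA key secondary endpoints treat a large flare simply as non-response. This also stands as corroboration of benefit. It does not correct the primary interval: the subgroup repeats use the same model, and responder rates answer a different question from the difference in means.

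Three stronger readings are tempting and are not supported:

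- A reader might infer that the planned interval is wrong. It is wrong only if the arm SDs differ.
- A reader might infer that the primary result will rest on a handful of outliers. The baseline EASI distribution is not given, and the example uses about the lowest baseline that entry allows.
- A reader might infer that a worsening tail leaves the trial underpowered. Any such figure needs an assumed outlier rate on top of an SD back-solved from the stated power, and the blacked-out SD may already include that tail.

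**Conclusion.** The point holds as a conditional weakness that is cheap to remove. As written, the model assumes equal variability in the two arms, on an endpoint and at an allocation where that assumption affects the interval, and no planned analysis of the mean difference relaxes it.

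In the one scenario linked to the Protocol's own figures (ratio about 1.2), the loss is about 1.5 points of coverage, 93.5% instead of 95%. That rests on the proportional-spread assumption and on treating the MMRM at Day 29 as a two-sample comparison with complete data. A ratio of 1.5 would cost 3.5 points, but it is hypothetical. Sensitivity of the mean to low-baseline flares is possible under the scoring rules; how often it would occur cannot be judged from the documents.

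**What to change.** In SAP 6.1.1.1, either estimate the covariance parameters separately by treatment arm or report empirical (sandwich) standard errors, and name the choice before unblinding. Keep the endpoint and the difference in means. If the sponsor judges this a major change to the primary analysis, carry it into Protocol 9.2.1 by amendment, as Protocol section 9 and SAP section 2 require.

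Optionally, add to SAP 6.1.1.2 one outlier-resistant sensitivity analysis of the primary endpoint, such as a rank-based analysis or an MMRM on log EASI. Every setting must be fixed in advance, including any constant added before taking logs, since that constant matters most at near-zero scores. Label it as targeting a different summary from the difference in means.

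The cost is one model option, plus one table if the optional analysis is added. The interval would be about 6% wider at a ratio of 1.2 (1/0.942 = 1.06) and about 7% narrower at 0.8 (1/1.076 = 0.93). At equal SDs it is essentially unchanged.
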